### **5.9.2 Non-pharmacokinetic data**

All available data will be included in the analyses and will be summarized as far as possible. Unless otherwise specified there will be no substitution of missing data, i.e. missing data will not be replaced, missing data will be handled as 'missing' in the statistical evaluation.

### **5.9.3 Handling of drop-outs**

Volunteers withdrawn from the study because of safety reasons or for reasons unrelated to the study medication will not be replaced.

## **5.10 Output from statistical analysis**

Complete SAS output will be given for all produced analyses as an Appendix to Statistical Report.

## 6. EVALUATION OF DEMOGRAPHICS AND BASELINE CHARACTERISTICS

Separate tables will be produced for SAD and for MAD parts of the study.

### 6.1 Patient Disposition

The number of patients will be presented for each treatment group. It will be displayed in Fig. “*Patient Disposition*”.

In addition, table will display the number and percent of patients included in the study as well as discontinuing patients for each treatment group and overall. This table will also contain the number and percentage of patients corresponding to the reason for discontinuation.

### 6.2 Demographics and baseline measurements

Baseline is defined as the last value prior to dosing. Absolute change from baseline will be calculated for all continuous safety parameters. Baseline demographic data will be tabulated and presented by dose.

Demographic data: age, height, weight and body mass index (BMI) will be summarized by descriptive statistics (n, mean, standard deviation, median, minimum and maximum), and gender and race, will be summarized by the number and percentage of subjects in each category in Table “*Demographics*”.

## **7. EVALUATION OF TREATMENT COMPLIANCE AND EXPOSURE**

### **7.1 Treatment Compliance**

Administration of investigational products will only be performed by authorized clinical research staff and will be followed by a hand and oral cavity check in order to confirm the swallowing of the product and fluid intake, if applicable.

Upon dispensing medication, the clinical research staff will record the related information on the applicable source documents, to allow investigational product accountability and evaluation of subject compliance.

### **7.2 Exposure to Study Drug**

The information regarding exposure to study drug will be listed accordingly in Listing “*Exposure to study drugs*”.

## 8. EVALUATION OF PHARMACOKINETIC PARAMETERS

### 8.1 SAD part

#### 8.1.1 General Consideration

The PK parameters will be derived individually for each volunteer from drug concentrations in blood samples. Values below or above the limit of quantification, if any, will be indicated as such and will be taken into account for the calculation of pharmacokinetic parameters after confirming or correcting the relevant value. Blood samples will be taken according to the schedule given in [Table 1](#) (see [Section 10.1](#) below).

Actual blood sampling time points will be used for individual calculations and presentations. Nominal times will be used for calculations and presentations of summarised data.

Descriptive statistics will be calculated for all PK parameters ( $C_{\max}$ ,  $t_{\max}$ ,  $AUC_{0-\text{last}}$ ,  $AUC_{0-\infty}$ ,  $\lambda_z$ ,  $\lambda_z$ ,  $CL/F$ ,  $V_z/F$ ) concentration-time data using Phoenix WinNonlin 8.3. A non-compartmental model will be assumed for all parameters. Linear regression analysis on the log-transformed concentrations for the determination of  $\lambda_z$  will be performed using at least 3-4 data points in the terminal phase, excluding  $C_{\max}$ . The terminal phase elimination rate constant  $\lambda_z$  will not be calculated if the terminal phase is not evident. Also, the square of the adjusted Pearson correlation coefficient for the goodness of the fit (coefficient of determination) of the regression line through the data points ( $R_{adj}^2$ ) must be 0.80 or higher, for the value of  $\lambda_z$  to be considered reliable. In cases where the  $\lambda_z$  rate is not assigned, the values of  $AUC_{0-\text{inf}}$  and  $t_{1/2}$  will not be estimated and will be reported as “Not calculated”. The value of  $AUC_{0-\text{inf}}$  will be considered unreliable but will be reported if the terminal area beyond the last quantified sample is greater than 20% of the total  $AUC_{0-\text{inf}}$ .

Graphical images will be given as individual and overlaying (pooled) plots by treatment. Linear and semi-logarithmic views will be produced.

All plasma concentrations and derived PK parameters for each treatment will be listed and summarized descriptively (mean values (arithmetic and geometric), standard deviations, minimum and maximum values, medians, and valid Ns for the calculated variables). Coefficient of variation (CV%) of the arithmetic and geometric mean values will also be presented. 95% CI for arithmetic mean will be given where possible.

#### 8.1.2 Computation formulas

Pharmacokinetic parameters will be calculated assuming a non-compartmental model as follows:

- $AUC_{0-t}$  (h.ng/mL) – The area under the plasma concentration versus time curve, from time 0 to the last measurable concentration, as calculated by the linear-up/log-down trapezoidal method. When concentrations are increasing (as in the absorption phase), the linear trapezoidal method will be used. When concentrations are decreasing (as in the elimination phase), the logarithmic trapezoidal method will be used. If  $C_i > C_{i-1}$  then:

$$AUC_i = AUC_{i-1} + \frac{C_i + C_{i-1}}{2} * (t_i - t_{i-1})$$

otherwise:

$$AUC_i = AUC_{i-1} + \frac{C_i - C_{i-1}}{\ln C_i - \ln C_{i-1}} * (t_i - t_{i-1})$$

where  $C_i$  is the value of observed plasma concentration at moment  $t_i$ . If the logarithmic trapezoidal rule fails in an interval due to lack of strict *monotonicity*, then the linear trapezoidal rule will apply for that interval.

- $AUC_{0-\infty}$  (h.ng/mL) The area under the plasma concentration versus time curve from time 0 to infinity, calculated as  $AUC_{0-\infty} = AUC_{0-t} + C_t/\lambda_z$ , where  $C_t$  is the last measurable concentration,  $\lambda_z$  is the terminal elimination rate constant.
- Residual area (%)  $\frac{(AUC_{0-\infty} - AUC_{0-t})}{AUC_{0-\infty}} \times 100\%$ .
- $C_{\max}$  (ng/mL) - Maximum measured plasma concentration over the time span specified.
- $t_{\max}$  (h) – Time of the maximum measured plasma concentration. If the maximum value occurs at more than one time point,  $t_{\max}$  is defined as the first time point with this value.
- $\lambda_z$  (1/h) – Apparent first-order terminal elimination rate constant calculated from a semi-log plot of the plasma concentration versus time curve. The parameter will be calculated by linear least-squares regression analysis using at least three points during the terminal log-linear phase, and “best fit” rule.
- $t_{1/2}$  (h) – Apparent first-order terminal elimination half-life will be calculated as  $t_{1/2} = \ln 2 / \lambda_z$ .
- $CL/F$  (L/h) – Apparent total body clearance following extravascular administration will be estimated as  $CL / F = \frac{Dose}{AUC_{0-\infty}}$ .
- $V_z/F$  - Apparent volume of distribution will be estimated as  $V_z / F = \frac{CL / F}{\lambda_z}$ .

### 8.1.3 Dose proportionality (SAD)

Dose-proportionality for PK parameters of OT and B-OT ( $AUC_{0-\infty}$ ,  $AUC_{0-last}$ , and  $C_{max}$ ) will be assessed by the power model [6]. The slope and the associated 90% CI will be reported. For the first 2 low doses where only 3 subjects are enrolled, no dose proportionality will be assessed. The key modelling assumption is that the logarithm of the PK variable is linearly related to logarithm of dose:

$$\log(PK \text{ parameter}) = \alpha + \beta \cdot \log(Dose) .$$

Let  $X_l$  is the lowest dose, and  $X_h$  is the highest dose, respectively. The predicted geometric mean of the highest dose is  $e^{\alpha} X_h^{\beta}$  and that of the lowest dose is  $e^{\alpha} X_l^{\beta}$  .. Dose proportionality may be defined as the ratio  $e^{\alpha} X_h^{\beta} / e^{\alpha} X_l^{\beta} = X_h / X_l$ , which can be rewritten

as:  $\left( \frac{X_h}{X_l} \right)^{\beta-1} = r^{\beta-1}$ , where  $r$  is the ratio of the highest dose to the lowest dose in the study.

Lower and upper limits may be defined as:  $g_l < \nu < g_h$ . This inequality solved for  $\beta$  gives the criterion for proportionality:  $1 + \frac{\ln(g_l)}{\ln(r)} < \nu < 1 + \frac{\ln(g_h)}{\ln(r)}$ .

Dose proportionality would be declared when the  $(1-2\alpha)*100\%$  CI for  $\beta$  lies entirely within the critical region:  $\left( 1 + \frac{\ln(g_l)}{\ln(r)}; 1 + \frac{\ln(g_h)}{\ln(r)} \right)$ .

Consequently, the dose proportionality of a certain exposure measure of the active ingredient for a given drug product can be concluded at the a significance level if the  $100(1-2\alpha)\%$  confidence interval for  $\beta$  is completely contained within critical region.

SAS/REG procedure will be used to estimate the regression coefficient and its 90% CI.

If the power model has failed to converge and the ANOVA has become the primary analysis, dose proportionality will be concluded if 90% confidence intervals for dose normalised Cmax and AUC are contained in the 80 to 125% range of the reference dose.

A reference dose as well as a maximal dose will be fixed by the Sponsor.

Following log-transformation, dose normalised AUC and Cmax will be analysed using a mixed model appropriate to the parallel study design. Each dose will be compared with the reference dose on a pairwise basis, linear contrasts will be used. The geometric mean ratios for each dose level will be compared to the reference dose. If the confidence intervals include unity, then there is no evidence to suggest the relationship between the test dose and the reference dose is not dose proportional. If the lower confidence interval lies only just below 1, this may be an indication that the true response at this level is slightly more than dose proportional compared to the reference dose level.

SAS/MIXED will be used to estimate ANOVA parameters.

---

 **Note.** For obtaining confidence intervals, the analysis of the raw ratio in the linear regression model relies on the use of Fieller's method, whereas it is straightforward in the power model. Also, the confidence intervals based on the power model are relatively narrower than with the ANOVA model because dose order and values are ignored in the latter [7].

---

---

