The SAD part of the study showed good tolerability and there were no side effects detected after once-daily administration of B-OT at an escalating dose ranging from 0.5 mg to 5 mg.

No B-OT was detected at any dose level in the plasma of the healthy volunteers.

At the maximum dose of 5 mg, the maximum concentration of OT in human plasma was 15.45 ± 3.76 ng/ml. The time to reach the maximum concentration ranged at the different dose between 1.67 ± 0.29 and 2.50 ± 1.18 hours.

Following single administrations of B-OT, the exposure to OT in terms of C_{max} and AUC_{0-t} increased with ascending doses from 0.5 to 5 mg in a slightly over proportional manner.

Further details can be found in the IB.

Study Rationale

This is a FIH clinical study and as such is conducted primarily to obtain information on safety, PK and PD properties of the tested compound. The scientific rationale of the study is based on the information that RNA viruses such as SARS-CoV-2 bring their own RNA polymerase into the cell. However, after infecting the cell and releasing their viral RNA, they depend on precursors necessary for replication of their viral RNA. The virus is dependent on ribose-5-phosphate (R5P) from the host cell as an essential building block for their replication.

The central switch for the regulation of cell cycle and cell proliferation as well as for the sufficient supply of R5P building blocks is provided by transketolase-like 1 (TKTL1) [Li et al., 2019], which therefore represents a good target for antiviral therapy.

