8.1.2 Treatment and observation period (SAD and MAD)

A total number of 24 subjects will be enrolled in the SAD part of the study in 5 cohorts:

Cohort 1 (0.5 mg B-OT): 3 subjects

Cohort 2 (1 mg B-OT): 3 subjects

Cohort 3 (2mg B-OT): 6 subjects

Cohort 4 (3 mg B-OT): 6 subjects

Cohort 5 (5 mg B-OT): 6 subjects

Each cohort will start with a sentinel subject (subject #1). Subject #2 - #3 or #2 - #6 of the same cohort will start treatment after a minimum of 48 hours if safety data indicate that dosing of subsequent subjects of this cohort is justified. Dose escalation to the next dose level will occur if three (first and second cohort) or six subjects (3 next cohorts) have completed the single dose treatment and if PK at Day 2 as well as safety data allow an escalation to the next dose level.

A total of 24 subjects will be enrolled in the MAD part of the study and assigned to multiple ascending dose groups in consecutive order:

Group 1 (1 mg B-OT): 6 subjects

Group 2 (2 mg B-OT): 6 subjects

Group 3 (3 mg B-OT): 6 subjects

Group 4 (5 mg B-OT): 6 subjects

Each cohort will start with a sentinel subject (subject #1). Subject #2 - #6 of the same cohort will start treatment after a minimum of 72 hours if safety data indicate that dosing of subsequent subjects of this cohort is justified. Dose escalation to the next dose level will occur if six subjects have completed the multiple dose treatment and if PK at Day 5 as well as safety data allow an escalation to the next dose level.

The health status of the trial subjects in the SAD and in the MAD part of the study will be assessed once again against the inclusion and exclusion criteria, as set by the study protocol, prior to study drug administration (Day -1). When considered suitable, the subjects will be assigned a unique study identifier and will be invited for treatment visit on day -1. Detailed description of all trial activities that need to be carried out are listed in the Visit and Assessment Schedule (Table 1 for the SAD part and Table 2 for the MAD part).

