14.9.1 Dose proportionality

Dose-proportionality for PK parameters of OT and B-OT (AUC_{0-inf}, AUC_{last}, and C_{max} for single dose, and AUC_{0-τ Day7}, and C_{max,ss} for multiple dose) will be assessed by the power model. The slope and the associated 90% CI based on the power model will be reported. For the first 2 low doses of the SAD part where only 3 subjects are enrolled, no dose proportionality will be assessed.

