## 8.2.5 Dose proportionality (MAD)

On Day 7, dose-proportionality for PK parameters of OT and B-OT ( $AUC_{0-\tau}$ , and  $C_{\max,ss}$ ) will be assessed by the power model [6]. The slope and the associated 90% CI will be reported. The same approach will be applied as for SAD ([sec.8.1.3](#)).

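### Leaving the 0.5 and 1 mg cohorts out of the SAD power model gives up as much as 81% of the slope information, and the dose-proportionality decision rule cannot be carried out as written

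*SAP*

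**What the plan says.** SAP 8.1.3 regresses the log of each PK parameter (AUC0-inf, AUC0-last, Cmax) on log dose and reports the slope with a 90% CI. It then restricts the doses: "For the first 2 low doses where only 3 subjects are enrolled, no dose proportionality will be assessed". Protocol 14.9.1 has the same rule: "For the first 2 low doses of the SAD part where only 3 subjects are enrolled, no dose proportionality will be assessed". The cohorts concerned are in protocol 8.1.2: "Cohort 1 (0.5 mg B-OT): 3 subjects" and "Cohort 2 (1 mg B-OT): 3 subjects". The remaining SAD cohorts are 2, 3 and 5 mg with six subjects each; SAP 4.1.1 still shows these three doses as to be determined. Protocol 6.1 already reports that OT exposure "increased with ascending doses from 0.5 to 5 mg in a slightly over proportional manner".

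SAP 8.1.3 also gives a decision rule. Proportionality is declared if the CI for the slope lies between 1 + ln(g_l)/ln(r) and 1 + ln(g_h)/ln(r), where r is the ratio of the highest to the lowest dose in the study. No values are given for g_l or g_h. The model is fitted with SAS REG. The alternative begins "If the power model has failed to converge and the ANOVA has become the primary analysis"; it then asks for CIs within 80-125% of a reference dose that the sponsor will fix, and adds a further reading rule: "If the confidence intervals include unity, then there is no evidence to suggest the relationship".

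SAP 8.2.5 applies the same approach to the MAD part: "On Day 7, dose-proportionality for PK parameters of OT and B-OT". Protocol 12.4.4 says B-OT will not be measured in the MAD part.

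**The concern.** A power model does not estimate each cohort separately. Every subject contributes to one slope, and subjects far from the mean log dose contribute most. The two excluded cohorts are the lowest doses and therefore among the most informative. Without them the analysed range falls from tenfold (0.5-5 mg) to 2.5-fold (2-5 mg), so the planned slope does not cover the range over which protocol 6.1 describes a slightly over-proportional increase.

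The decision rule is a separate problem. Without g_l, g_h and a consistent r, two analysts could reach opposite conclusions from the same slope and CI. The alternative analysis would not rescue a badly fitting power model, because its trigger is unrelated to fit. SAP 5.2 marks the assessment of statistical assumptions as not applicable, so no other check of log-linearity is planned.

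**Working it through.** **Inputs.** SAD doses and cohort sizes are from protocol 8.1.2: 0.5 mg (3), 1 mg (3), 2 mg (6), 3 mg (6), 5 mg (6). The total is 2×3 + 3×6 = 24, which agrees with SAP 3.2.1. The documents give no precision or power figure for the slope, so there is none to reproduce. For illustration, the CV comes from the 5 mg Cmax in protocol 6.1, 15.45 ± 3.76 ng/ml. Taking ± as an SD, 3.76/15.45 = 24.3%, and σ on the log scale = √ln(1 + 0.243²) = 0.240. A range of 15-40% is also shown.

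**Slope information.** Var(slope) = σ²/Sxx, with Sxx = Σ nᵢ(ln dᵢ − mean ln d)².

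| Doses fitted | N | Sxx | SE at CV 24% | 90% CI half-width |
|---|---|---|---|---|
| 2, 3, 5 mg (planned) | 18 | 2.53 | 0.151 | 0.26 |
| 1, 2, 3, 5 mg | 21 | 5.84 | 0.099 | 0.17 |
| 0.5, 1, 2, 3, 5 mg | 24 | 13.11 | 0.066 | 0.11 |

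The half-width is t(0.95, N−2) × σ/√Sxx; for the planned fit, 1.746 × 0.240/√2.53 = 0.26.

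- Loss from the exclusion: 1 − 2.53/13.11 = 81%. This does not depend on the CV.
- Gain from all five doses: 13.11/2.53 = 5.2-fold.
- Gain if the 0.5 mg cohort is not evaluable: 5.84/2.53 = 2.3-fold.
- Share of the full Sxx from the three 0.5 mg subjects: 3 × (ln 0.5 − 0.764)²/13.11 = 49%.

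Half-widths at other CVs, all five doses versus planned: 15%, 0.07 v 0.16; 20%, 0.09 v 0.22; 30%, 0.14 v 0.32; 40%, 0.18 v 0.42.

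For the highest-to-lowest ratio r^(slope−1), a half-width of 0.26 over r = 2.5 is a factor of about 2.5^0.263 = 1.27. A half-width of 0.11 over r = 10 is about 10^0.114 = 1.30. The all-dose fit thus describes a tenfold range with nearly the precision the planned fit gives for a 2.5-fold range.

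**Decision rule.** With symmetric limits, g_l = 1/g_h, the region is 1 ± ln(g_h)/ln(r). The SAP text gives r = 5/0.5 = 10; the analysed doses give r = 5/2 = 2.5. The last column is simulated for the 2-5 mg data with a true slope of 1 and CV 24%.

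| g_h (assumed) | Region, r = 10 | Region, r = 2.5 | Declared, r = 2.5 |
|---|---|---|---|
| 1.25 | 1 ± 0.097 | 1 ± 0.244 | about 6% |
| 1.5 | 1 ± 0.176 | 1 ± 0.443 | about 76% |
| 2.0 | 1 ± 0.301 | 1 ± 0.756 | over 99% |

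The same truth and the same data are declared proportional anywhere from about 6% to over 99% of the time, depending on a number the SAP does not state.

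**Fallback trigger.** The regression has two parameters. With doses 2, 3 and 5 mg the design matrix has rank 2, so least squares has a closed-form solution. Nothing iterates, and nothing can fail to converge. If an analyte has no data (protocol 6.1 reports no B-OT detected at any SAD dose), the ANOVA cannot be fitted either.

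**The case against.** The strongest objection is that the low-dose data may be poor and the gain smaller than 5.2-fold. Protocol 8.1 notes very low OT concentrations at 0.5 mg. SAP 8.1.1 leaves AUC0-inf uncalculated where the terminal slope is not assigned. Half of the full Sxx comes from three subjects, and one CV taken from Cmax at 5 mg need not hold at other doses or for AUC. This stands: 81% is an upper figure and the influence of the 0.5 mg cohort must be checked. Even without that cohort, adding 1 mg more than doubles the information.

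A second objection is that changing the primary fit now is post hoc, since SAP 5.8 says the SAD PK data were analysed before the MAD part began and protocol 6.1 reports the trend. This also stands, which is why the all-dose fit should appear beside the 2-5 mg fit with the timing disclosed.

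Third, the impact is bounded. The study is exploratory and PK is secondary; every SAD dose is still summarised descriptively; protocol 8.6.1 bases escalation on committee review of safety and emerging exposure, not on this slope. The slope and 90% CI, which matter most, are already planned.

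A reader might infer that the rule is almost certain to fail even under exact proportionality. The documents do not support that. It requires 80-125% limits, which the SAP attaches only to the ANOVA, and wider limits reverse the result. A reader might also infer that the reference dose will be chosen in the light of the SAD results, but SAP 8.1.3 gives no date for fixing it. The two ANOVA reading rules are not strictly contradictory, because one concludes proportionality and the other only finds no evidence against it; how often either is met matters little for an analysis that cannot start.

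**Conclusion.** The point holds on two counts. First, for the SAD part only, excluding 0.5 and 1 mg gives up as much as 81% of the slope information and narrows the assessed range to 2-5 mg. At CV 24% the 90% CI half-width is about 0.26 rather than 0.11. This takes the sentence to mean that both cohorts leave the regression, that all 24 subjects are evaluable, and that log-scale variance is constant across doses. The MAD part keeps 1, 2, 3 and 5 mg with six subjects each (Sxx 8.31) and loses nothing here.

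Second, for both parts, the declaration rule cannot be executed: the limits have no values, r is not tied to the doses analysed, and the fallback has a trigger that cannot occur. The defect is that the rule is unspecified, not that it is known to be too strict. Adding doses does not make a declaration easier. With assumed 80-125% limits, the chance under exact proportionality at CV 24% would be about 2% with five doses against 6% with three, because the region narrows as r grows. The case for the all-dose fit is better estimation.

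Listing B-OT for Day 7 in SAP 8.2.5 is a wording slip: SAP 2.2 names only OT for MAD dose proportionality.

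**What to change.** 1. In SAP 8.1.3 and protocol 14.9.1, fit the power model to all evaluable SAD subjects (0.5-5 mg) and report it beside the 2-5 mg fit. State that the all-dose fit was added after the SAD PK results were known.
2. Use Cmax, and either AUC0-inf where the terminal slope is reliable or AUC over a window that is quantifiable at every dose. AUC0-last can stop earlier at low doses and steepen the slope. Refit without the 0.5 mg cohort to show its influence.
3. Report the slope, its 90% CI, and r^(slope−1) with its CI, taking r from the doses analysed. Delete the declaration wording for both SAD and MAD.
4. Replace the convergence trigger with a lack-of-fit check, such as a quadratic term in log dose, or delete the fallback. In either case remove the rule based on the CI including unity.
5. Delete B-OT from SAP 8.2.5.

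The cost is SAP wording and one line in protocol 14.9.1, with no new SAD data. The price is that the all-dose SAD fit is post hoc, and that it leans on small, high-leverage cohorts that may have more values below the limit of quantification.
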